## Abbreviations

ACC	American College of Cardiology
ACG	American College of Gastroenterology
AHA	American Heart Association
ACS	Acute Coronary Syndrome
AE	Adverse Event
ASCVD	Atherosclerotic Cardiovascular Disease
CABG	Coronary Artery Bypass Grafting
CAD	Coronary Artery Disease
CCs	Chronic Coronary Syndromes
CRF	Case Report Form
CVD	Cardiovascular Disease
CPIC	Clinical Pharmacogenetics Implementation Consortium
DAPT	Double Antiplatelet Treatment
DPWG	Dutch Pharmacogenetics Working Group
EACTS	European Association for Cardio-Thoracic Surgery
EMA	The European Medicines Agency
ePCI	elective Percutaneous Coronary Intervention
ESC	European Society of Cardiology
ESH	European Society of Hypertension
ESVS	European Society for Vascular Surgery
FDA	U.S. Food and Drug Administration
GCP	Good Clinical Practice
HF	Heart Failure
ICD-10	10 th version of the International Classification of Diseases
IRB	Institutional Review Board
MACE	Major adverse cardiovascular event
MACCE	Major adverse cardiac and cerebrovascular event
MI	Myocardial Infarction
mut	mutant allele
NACE	New Adverse Clinical Event
NCDC	National Centre for Disease Control and Public Health
NSAIDs	Nonsteroidal Anti-inflammatory Drugs
PCI	Percutaneous Coronary Intervention
PCR	Polymerase chain reaction
P2Y12	G protein-coupled purinergic receptors of G i class, adenosine diphosphate chemoreceptor
Rc	Frequency of occurrence of a control event (statistical calculation value)
Rt	Frequency of occurrence of an experimental event (a statistical calculation quantity)
RT-PCR	Real-Time Reverse Transcription–Polymerase Chain Reaction Assay
SAE	Serious adverse event
STE/NSTE-ACS	ST-Elevation or Non-ST-Elevation Acute Coronary Syndrome
wt	wild trait allele

## SYNOPSIS

Title	The research implementation of the clinical model for evaluating CYP2C19 allele genotype-guided clopidogrel treatment.
Sponsor	Vistamedi Ltd. [name]. phone: [name], [name]; Email: [contact]
Co-funder	International Federation of Clinical Chemistry and Laboratory Medicine (IFCC). [name]; Email: [contact]
Sites	4 or more clinical practice centers that provide clinical case management of ACS and CCS, PCI procedures or post-PCI and follow-up activities for patients at risk of CVDs, including CAD, HF.
Relevance	
Among the challenges of ASCVD, preventing recurrent MACCEs is a significant issue. Scientific evidence widely supports pharmacotherapeutic approaches for the routine use of a P2Y12 inhibitor (clopidogrel or an alternative) within the framework of DAPT or other regimens of antiplatelet treatment. Clopidogrel remains the most commonly used P2Y12 inhibitor in the post-PCI setting. Pharmacogenetic models of drug selection are also being introduced to optimize treatment.
 
Currently, the selection of treatment with clopidogrel or an alternative P2Y12 inhibitor by genotyping CYP2C19 alleles is based on reliable evidence. The effects of treatment are influenced by the wide variability of CYP2C19 genotype in the population, which, even under conventional treatment with clopidogrel, significantly increases the risk of MACCEs in carriers of non-functional alleles.
 
The antiplatelet treatment paradigm faces a significant dilemma regarding the use of clopidogrel: on the one hand, existing practice guidelines (ESCARDIO and ACC/AHA) recommend the use of clopidogrel without CYP2C19 genotyping. On the other hand, the Global Consensus Report of Industry Associations on the Possibility of Adapting P2Y12 Inhibitor Treatment to CYP2C19 Genotyping and the Selective Use of the Test (2019), as well as the FDA's so-called "black box warnings" on the use of clopidogrel, the EMA's precautionary statements, the CPIC and DPWG scientific reports and practice guidelines, and the evidence base UNC study, TAILOR-PCI, POPular Genetics, PHARMA-ACS, UK Biobank study, and other so-called "From New Prospective Studies" clearly demonstrates the advantages for guiding P2Y12 inhibitor treatment by CYP2C19 genotype.
 
In these circumstances, promising research directions are determined by the following critical questions: Is it possible to select P2Y12 inhibitor treatment by genotype? This issue will be resolved by answering the main question: Are CYP2C19 genetic variations associated with clinical outcomes of clopidogrel treatment, in interaction with other known influencing factors or independently of them?

Hypothesis	
The research question is how antiplatelet treatment for preventing major adverse cardiovascular events after ePCI works in chronic coronary artery disease when guided by personal genetic characteristics for drug metabolism.
 
The study aims to test two research hypotheses:
 
 
• CYP2C19 genotype-guided clopidogrel treatment ensures better clinical outcomes when compared with conventional treatment selection led without CYP2C19 genotyping.
 
• CYP2C19 genotype-guided antiplatelet treatment could be beneficially applied in real-world clinical practice.
 

Design	Multicenter, randomized, parallel-group controlled study

Primary Objectives	
The aim of the study is to evaluate CYP2C19 allele genotype-guided antiplatelet treatment outcomes.
 
The specific objectives of the study are:
 
 
— Pre-assignment and randomization of study participants into study arms for conventional and CYP2C19 genotype-guided antiplatelet treatment with clopidogrel or an alternative P2Y12 inhibitor;
 
— providing RT-PCR-based pre-, analytical and post-analytical processes of the study to ensure CYP2C19 *2, *3 allele profiling for detection of study participants with normal functioning (NFA) and loss of function (LOF) allele;
 
— Observation of clinical outcomes of patients in the study groups during the 12 months of treatment;
 
— Evaluation of processes and non-clinical outcomes of clinical case management;
 

Secondary Objectives	
 
— Implementation of the methods and procedures provided by the research protocol into a real clinical practice pipeline;
 
— Raising awareness and understanding of the role of laboratory services by bridging clinical, laboratory practice professionals and other stakeholders to achieve patient-centeredness and improve clinical outcomes;
 
— Evaluation of clinical practice models based on assessments of molecular markers;
 
— Disseminate study results through publishing a scientific paper in a peer-reviewed journal and abstracts for reporting study results.
 

Study Participants	
240 patients requiring antiplatelet treatment with a P2Y12 inhibitor after ePCI as a major cardiovascular clinical event for CAD, meeting clinical inclusion criteria and not meeting exclusion criteria.

Randomization	
Inclusion in two parallel groups with a 1:2 allocation ratio of controls (active comparators) and experiments. Genotyping the CYP2C19 *2, *3 alleles of experimental arm participants for separation of carriers of normal *2, *3 function alleles (NFA) and Carriers of loss of function *2, *3 alleles (LOF).

Study arms	
3 arms of study participants:
 
1st arm - experimental: "Normal Metabolizers of Clopidogrel", 110 study participants diagnosed with chronic coronary artery disease who had undergone elective PCI, tested with CYP2C19 genotyping and identified as NFA *2, *3 carriers, who undergo CYP2C19 Genotype-Guided Clopidogrel Treatment - Clopidogrel as a component of preventive antiplatelet treatment such as double antiplatelet treatment (DAPT), or an antiplatelet drug (clopidogrel) combined with the non-vitamin K antagonist oral anticoagulants (NOAC), incl. triple antiplatelet treatment (Aspirin, Clopidogrel and a NOAC), or antiplatelet monotherapy (Clopidogrel).
 
2nd arm - experimental: "Passive Metabolizers of Clopidogrel", approximately‡ 50 study participants diagnosed with chronic coronary artery disease who had undergone elective PCI, tested with CYP2C19 genotyping, identified as LOF *2, *3 allele carriers, who undergo CYP2C19 Genotype Guided Antiplatelet Treatment Alternative to Clopidogrel - an antiplatelet drug alternative to clopidogrel in conventional dosing regimen, as a component of preventive antiplatelet treatment, such as double antiplatelet treatment (DAPT) with ticagrelor or prasugrel, or prasugrel combined with the nonvitamin K antagonist oral anticoagulants (NOAC), or antiplatelet monotherapy (ticagrelor, or prasugrel).
 
3rd arm - active comparator: "Unspecified Metabolizers of Clopidogrel", 80 participants diagnosed with chronic coronary artery disease who had undergone elective PCI were allocated to the arm, without CYP2C19 genotyping through simple randomization, and having an unspecified metabolism phenotype, who were assigned to the conventional

	
clopidogrel treatment - clopidogrel as a component of preventive antiplatelet treatment, such as double antiplatelet treatment (DAPT), or clopidogrel combined with the non-vitamin K antagonist oral anticoagulants (NOAC), incl. triple antiplatelet treatment (Aspirin, Clopidogrel and a NOAC), or antiplatelet monotherapy (Clopidogrel).
 
† in the Georgian population, the prevalence of CYP2C19 LOF carriers has not been studied and is unknown. For preliminary calculations of the study participants' number in the 1st arm and 2nd arm, known data from the European population study were used [21].

Controls	
2 study arms could be used for controlling participants' (study) outcome measures: 3rd study arm participants create the active comparators group for 1st and 2nd arm, and besides, 2nd study arm participants - as the comparators for 1st arm.
 
Control 1: "Normal Metabolizers of Clopidogrel" - 110 study participants vs "Unspecified Metabolizers of Clopidogrel" - 80 participants;
 
Control 2: "Passive Metabolizers of Clopidogrel" - approximately 50 participants vs "Unspecified Metabolizers of Clopidogrel" - 80 participants;
 
Control 3: "Normal Metabolizers of Clopidogrel" - 110 study participants vs "Passive Metabolizers of Clopidogrel" - approximately 50 participants.

Selection criteria	
Participants of both sexes aged between 35-79 years are eligible for the study.
 
Inclusion Criteria:
 
 
▪ Diagnosed with chronic coronary artery disease;
 
▪ Completed informed consent form for participation in the study;
 
▪ Undergone elective PCI within the last 12 weeks without procedure-related complications; or the clinical challenge is to de-escalate post-PCI antiplatelet treatment from an alternative P2Y12 inhibitor to clopidogrel.
 
▪ LVEF<math>\geq</math>38% after index PCI;
 
 
Exclusion Criteria:
 
 
▪ Concomitant using of potent CYP3A4 or CYP2C19 inhibitors;
 
▪ Clinical obesity, BMI - 40 kg/sq.m or more;
 
▪ Type 1 diabetes mellitus;
 
▪ Poorly controlled type 2 diabetes mellitus, Hba1c - 9% or more;
 
▪ Acute Myocardial Infarction;
 
▪ Coronary artery bypass grafting was performed within the last 12 weeks.
 
▪ Valvular heart disease due to dysplasia, connective tissue disorders, or inflammatory disorders, or valvular disorders requiring cardiac surgery;
 
▪ History of severe hepatic impairment;
 
▪ Severe chronic kidney disease;
 
▪ Clinically important leucopenia, lymphopenia, thrombocytopenia or thrombocytosis;
 
▪ History of hemorrhagic diathesis or coagulopathy;
 
▪ An active or an obvious threat of bleeding (including GI bleeding):
 
▪ Bleeding within the past 6 months that required hospitalization;
 
▪ Blood transfusion during the past 6 months or its refusal;
 
▪ History of intracranial hemorrhage;
 
▪ Cardiac or non-cardiac degenerative disease, including: cardiomyopathy, restrictive lung disease, or neurodegenerative diseases;
 
▪ Malignant tumor (cancer) that limits life expectancy to less than one year;
 
▪ Current chemotherapy or immunosuppressive therapy;
 
▪ Ongoing immunosuppression or immunosuppressive conditions;
 

	
 
▪ Pregnancy or lactation period;
 
▪ Any disease/condition for which control is not achieved;
 
▪ Personal (patient/physician dependent) or health care system-related circumstances that can restrict or limit any study procedures or operations.
 

Product	
Selection of P2Y12 inhibitor treatment by CYP2C19 allele genotype.
 
The investigational product development is based on the RT-PCR-based detection of normal or loss-of-function alleles of the human cytochrome P450 system 2c19 enzyme encoded by CYP2C19 *2, *3.

Expected use	
Tailoring antiplatelet treatment to optimize MACCEs prevention in high-risk ASCVD patients.

Perspective arm	
A clinical group of patients with ASCVD who require treatment with a P2Y12 inhibitor (including clopidogrel) after PCI for acute myocardial infarction, characterized by a more severe course of the disease and a significantly higher baseline risk of recurrent MACCEs compared with the participants group under the study. The perspective arm is clinically more heterogeneous and requires a different study design.

Duration of the study	
Total duration of the study: 24 months.
 
 
▪ Expected duration of the study activities (from screening/randomization of the first patient to the end of follow-up of the last involved patient): 20 months; 
 
— Patient enrollment period: 8 months;
 
— Follow-up period: 12 months;
 
 
 
▪ Study preparation period: 2 months;
 
 
Study closure period: 2 months.

Follow-up	
Follow-up of study end-points from the start of the study intervention:
 
 
▪ 3 months (<math>\pm 1</math> week);
 
▪ 6 months (<math>\pm 1</math> week);
 
▪ 12 months (<math>\pm 1</math> week);
 
 
Follow-up evaluation within 72 hours in cases of early withdrawal within 12 months from the study for any reason.
 
Reasons for the early withdrawal are defined as:
 
 
▪ Withdrawal by study participant;
 
▪ Non-compliance with treatment intervention;
 
▪ Loss of follow-up;
 
▪ Physician's decision.
 
 
Routine observations of the study cases by the institutional standards and protocols for long-term disease control, as accepted for the real practice of clinical centers enrolling the study participants.

Clinical management and medication treatment	
The ongoing management and treatment of patients in the study group, as well as those withdrawn from the study following the ESC, ESC/ESH, ESC/EACTS, ESC/ESVS, ACC/AHA, ACC/AHA/ASA, ACG, ISTH guidelines and recommendations for CAD and concomitant ASCVDs.
 
Treatment of other concomitant diseases/conditions following the recommendations provided by national protocols and guidelines, and taking into account the contraindications and limitations of the use of individual medications.

Primary clinical end-points for outcome measures	
 
— Death from any cause within a 12-month of the study follow-up;
 
— Death from any cardiovascular cause within a 12-month of the study follow-up;
 

Secondary clinical end-points of outcome measures	
 
— Non-fatal myocardial infarction within a 12-month of the study follow-up;
 
— Unstable angina or angina requiring hospitalization within a 12-month of the study follow-up;
 
— Stroke or transitory cerebral ischemic event within the study follow-up period within a 12-month of the study follow-up;
 
— Major bleeding within a 12-month of the study follow-up;
 
— Non-major bleeding within a 12-month of the study follow-up;
 
— Heart failure event within a 12-month of the study follow-up;
 
— Percutaneous coronary intervention or coronary artery bypass-grafting within a 12-month of the study follow-up
 

Other end-points of outcome measures	
 
— Composite of death from any cause, non-fatal myocardial infarction, stroke, or major bleeding within a 12-month of the study follow-up (Net adverse clinical events - NACEs);
 
— Composite of death from any cause, non-fatal myocardial infarction, or stroke within a 12-month of study follow-up (Major adverse cardio or cerebrovascular events - MACCEs);
 
— Composite of death from cardiovascular cause, non-fatal myocardial infarction, recurrent angina, or repeated revascularization (PCI or CABG) within a 12-month of study follow-up (Major adverse cardiovascular events - MACEs);
 
— Number of study participants whose health status was defined as good or satisfactory, or with the appearance of CVD symptoms, or with a significant inability to self-care (Patient-Reported Health Status) reported by the patient or patient caregiver at 3, 6 and 12 months of the study follow-up;
 
— Participants self-reported (or patient's caregiver reported) angina not required hospitalization (Patient-Reported Angina Not Required Hospitalization at 3, 6 and 12 months of the study follow-up;
 
— Participants reported (or patient's caregiver reported) last week's shortness of breath due to heart failure not requiring hospitalization (Patient-Reported Heart Failure Severity) at 3, 6 and 12 months of the study follow-up;
 
— Withdrawal for any reason within a 12-month of the study follow-up;
 
— Costs of clinical service utilization for case management during the study follow-up;
 
— Incremental costs incurred for real-world health care services, including costs for the MACCEs, MACEs and NACEs;
 

Other measures	
 
— Cardiometabolic risk factors and their control status;
 
— Total number of hospitalizations for any reason within 12 months of the study follow-up;
 
— Comorbidities;
 

Safety	
The risk of the study is minimal. The clinical diagnostic procedures for screening, randomization (incl. CYP2C19 *2, *3 allele genotyping) and follow-up are safe for study participants.
 
Health-related risks are associated with major adverse cardio- and cerebrovascular risks (MACCEs) of the CAD and possible known adverse effects of the drugs used in medication control of the diseases/conditions. However, they cannot be significantly related to adverse events/effects caused by the study procedures.
 
They can appear in the routine processes of clinical case management outside the scope of the study activities in real clinical practice. The follow-up assessments at the 3rd, 6th and 12th month follow-up and the selection and management of medication treatment provided across the study are likely to reduce the risks.

	
Equally, risks to the health of study participants can be contributed to or neutralized by medical care procedures provided in real practice outside the scope of the study, because on the one hand, it may be erroneous or incomplete, on the other hand, it may be timely and targeted.
 
Risks to the health of study participants can be attributed to non-compliance with clinical management and treatment measures. The study's follow-up assessment processes can effectively prevent these risks.
 
Threats may arise from possible violations of the confidentiality of study participants and possible illegal access to and processing of personal data. Consistently conducted study procedures provide special measures to protect confidentiality and personal data.
 
Deviations in the implementation of procedures and activities may cause study-related risks. However, ongoing monitoring of research processes will make it possible to assess and prevent risks caused by research deviations.
 
Researchers/investigators, the management team and the IRB will carry out research risk assessments and mitigation measures.

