#### **1.4.3 Expected Duration of the Study**

The total expected duration of the study is 24 months. The implementation will conditionally include 4 stages.

Preparatory work will be carried out during the first 2 months of the project implementation to initiate the study.

[figure not shown]
The expected duration of the study component itself is 20 months from the screening/randomization of the first study participant to the end point of observation of the last involved study participant.

During this period, the inclusion of participants in the study will continue for approximately 8 months.

Follow-up visits and relevant examinations will begin 1 month after the inclusion of the first patient, which will continue for 12 months after the inclusion of the last participant in the study and continue throughout the follow-up of clinical outcomes and related clinical case management processes.

The analysis of the final results of the study, the formulation of assessments, the preparation of the scientific paper, submission for peer-reviewed publications and the preparation of the final scientific and technical reports of the study will be carried out during the last 2 months of the project.

Monitoring and evaluation activities will be carried out throughout the 24-month project period.

The overall duration of the research project can be reduced by condensing the study components separately. In particular, the intensification of study participants' enrolment activities can be achieved by increasing the frequency (accelerating) of study participants' screening, pre-assignment and randomization in study centers and, accordingly, by shifting the calendar end of the follow-up component period. In such a case, it is expected that the reasonable duration of the calendar term for the study activities for study participants enrollment will be 6 months instead of 8 months, and accordingly, by shifting the calendar end of the 12-month follow-up period, the overall duration of the research project will be shortened up to 22 months instead of 24 months.

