### 2.3.2 Structural Design

Study participants will be recruited from 4 or more clinical centers. Based on informed consent, these centers will be selected and employed to provide study-specific activities under the condition that they provide CAD-specific diagnostic, treatment, and prevention services as recommended by current guidelines in their real-world clinical practice. They must provide GCP-compliant care based on current quality standards, patient best interests, and safety.

A logical model of study.

A population of patients who require antiplatelet therapy with a P2Y12 inhibitor following ePCI in CAD CCS cases within the framework of the recommendations for the use of DAPT (ESC, ACC/AHA) will be pre-assigned from the centers' real-world practice. Eligible patients will be considered for participation in the study after formal informed consent for inclusion in the specific clinical study measures.

Screening measures will be implemented for these patients to establish study inclusion and exclusion criteria. In conditions of the existence of inclusion criteria and absence of exclusion criteria, study participants will be randomized to the study or control arm by control-to-experiment allocation rate 1:2.

Study participants randomly allocated to the experimental arm will undergo laboratory blood testing for CYP2C19 \*2, \*3 genotyping using the RT-PCR-based allele discrimination method. According to the results of genotyping, the study participants will be assigned to two experimental treatment arms:

1st experimental arm will consist of the study participants with the active metabolizing phenotype of CYP2C19 (a normal function CYP2C19 \*2, \*3 allele (NFA) genotype), who will receive clopidogrel-based antiplatelet treatment;

2nd experimental arm will consist of study participants with the passive metabolizing phenotype of CYP2C19 (a loss-of-function CYP2C19 \*2, \*3 allele (LOF) genotype, heterozygous or homozygous), who will receive alternative antiplatelet treatment of clopidogrel.

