Study participants allocated to the control arm – 3rd arm of active comparators will not undergo laboratory blood testing for CYP2C19 \*2, \*3 genotyping, will be considered as study participants with unspecified metabolizing phenotype of CYP2C19 and receive the P2Y12 inhibitor clopidogrel-based antiplatelet treatment according to current clinical practice recommendations, without genotyping for CYP2C19 \*2, \*3 alleles as by real-world practice.

All study participants assigned to the study arms will undergo baseline and ongoing clinical follow-up to assess clinical endpoints as study clinical outcomes.

All clinical cases will be followed up with the primary, secondary and other prespecified clinical endpoints of the study and routine clinical indicators of safety at 3, 6, and 12 months. Non-clinical study outcomes will be assessed and compiled with other results of the outcome measures.

Study monitoring and evaluation procedures will be implemented alongside the study activities to assess safety and efficacy, and outputs.

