It is reasonable to assume that 75% of the selected study subjects will complete the study activities in full by 12 months of follow-up after enrollment. A portion of the 25% of patients are expected to drop out of the study for various reasons. Withdrawal by study participants, non-compliance with treatment, loss to follow-up and physician decisions are expected as the possible reasons for the study's non-completion.

Some of the dropped-out study participants will undergo appropriate clinical assessments at the interim follow-up periods (before 3, 6, or 12 months) or at the time of early withdrawal from the study and are therefore also considered a source of study data.

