The procedures of the post-analytical stage of the laboratory study include the analysis of the measurement results obtained at the RT-PCR stage, the formation of the final test result, and the documentation of the study result in the form of a report.

The laboratory study report will be transmitted to the researcher, authenticated in the study and the patient. The study investigator will enter the result reflected in the report into the clinical case registration form.

After that, the remains of the biological material sample will be destroyed according to the procedures adopted in the laboratory.

During the initial assessment and follow-up period, blood and urine samples of the study participants involved can be collected and processed by the medical care team and the study center investigator for various laboratory-diagnostic tests as part of the ongoing clinical assessments - at the end of the 3rd, 6th and 12th months and in case of early withdrawal of the participant from the study or at any time during the follow-up. These laboratory tests may be performed as routine diagnostic tests in real-world practice in an accredited diagnostic laboratory of the study center or other medical institution using conventional (generally accepted) methods for performing these tests.

The results of the tests performed in the laboratory of the study center or other medical institution within the follow-up period can be collected in the patient's outpatient medical record as a routine practice. The investigator may transfer the results of these diagnostic tests to the study case registration form and then use them for the purposes of the study.

The patient's outpatient medical record will also include the results of other laboratory tests used for routine management of the patient's condition, which are not of interest to the study, although they can be used to characterize the study's endpoints.

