The hazard ratio (HR) of death from any cause for study participants of 'normal metabolizer' and 'passive metabolizer' vs 'unspecified metabolizer' study participants	Numerator: the hazard rate from any cause of death of 'normal metabolizer' study participants, calculated as the proportion of any cause of death among 'normal metabolizer' and 'passive metabolizer' study participants Denominator: the hazard rate from any cause of death of 'unspecified metabolizer' study participants, calculated as the proportion of any cause of death (%) among 'unspecified metabolizer' study participants
The relative risk (RR) of developing death from any cause for 'normal metabolizer' study participants' arm vs 'unspecified metabolizer' study participants' arm	Numerator: the probability of developing death from any cause in the 'normal metabolizer' study participants arm, calculated as the number of 'normal metabolizer' study participants dead from any cause divided by the sum of the number of 'normal metabolizer' study participants dead from any cause and number of 'normal metabolizer' study participants not dead from any cause; Denominator: the probability of developing death from any cause in the 'unspecified metabolizer' study participants' arm, calculated as the number of 'unspecified metabolizer' study participants dead from any cause divided by the sum of the number of 'unspecified metabolizer' study participants dead from any cause and number of 'unspecified metabolizer' study participants not dead from any cause;
The relative risk (RR) of developing death from any cause for aggregated 'normal metabolizer' and 'passive metabolizer' study participants' arms vs 'unspecified metabolizer' study participants' arm	Numerator: the probability of developing death from any cause in the aggregated 'normal metabolizer' and 'passive metabolizer' study participants arm, calculated as the aggregated number of 'normal metabolizer' and 'passive metabolizer' study participants dead from any cause divided by the sum of the aggregated number of 'normal metabolizer' and 'passive metabolizer' study participants dead from any cause and aggregated number of 'normal metabolizer' and 'passive metabolizer' study participants not dead from any cause;

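### Endpoint follow-up has three different time origins, none of them stated to be randomisation, and guided participants without a genotype result drop out of every guided-versus-control row while no control can

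*Combined protocol and SAP*

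**What the plan says.** **Time origin.** Three places give three anchors.
- Synopsis, Follow-up: "Follow-up of study end-points from the start of the study intervention", with visits at 3, 6 and 12 months.
- Section 1.4.3, on follow-up visits: "which will continue for 12 months after the inclusion of the last participant in the study".
- Section 2.4.2: 75% of participants "will complete the study activities in full by 12 months of follow-up after enrollment".

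**Order of steps in the guided group.** Section 2.3.2: "Study participants randomly allocated to the experimental arm will undergo laboratory blood testing for CYP2C19" *2 and *3. After that, "According to the results of genotyping, the study participants will be assigned to two experimental treatment arms". Section 2.5.9 describes collection at the centre, transport to a single laboratory and analysis. It then says "The laboratory study report will be transmitted to the researcher". No turnaround time is given.

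**Control group.** Under section 2.3.2, controls "will not undergo laboratory blood testing for CYP2C19" alleles, so their arm is fixed by randomisation. The date on which their study intervention starts is not defined.

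**Analysis groups.** Appendix 3 defines rates by metabolizer group. The guided side of the pooled relative risk for death is "the probability of developing death from any cause in the aggregated 'normal metabolizer' and 'passive metabolizer' study participants arm", and the other pooled rows follow the same pattern. No section defines an as-randomised analysis set or says how an event before the genotype report is counted.

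**The concern.** The pooled Appendix 3 rows are the only ones that could compare the two groups as they were randomised. As defined, they compare genotyped guided participants with all controls. Membership of the guided side depends on something that happens after randomisation, namely remaining in the study until a usable report arrives. Section 3.2.6 adds to this: a participant is withdrawn once a MACCE or anticipated adverse medication effect is registered, which could happen before an arm exists.

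The time origin raises a second, conditional problem. If controls start their intervention at randomisation, the Synopsis wording counts a control event during the first days but puts a guided event on the same day before the guided clock starts. Separately, three anchors allow centres to place the month-12 cut-off at different dates.

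Both problems reach the two primary death endpoints. The Synopsis (Effectiveness) and section 2.5.7 rely on random allocation to control bias, and that protection holds only if everyone randomised is analysed from the same starting point.

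**Working it through.** **The plan's own figure.** Section 2.6.2 gives a minimum of 221 (0.6 vs 0.4, 1:2, two-sided 0.05, power 0.8). With pooled variance, the average event probability is (0.6 + 2×0.4)/3 = 0.467. Controls needed = [1.96·√(1.5×0.467×0.533) + 0.842·√(0.24 + 0.24/2)]² / 0.2² = 72.5, so 73. Then 73 + 146 = 219, in line with 221. Time zero does not enter this formula, so correcting it leaves the sample size unchanged.

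**Who is missing from which row.**

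| Participant | Arm-level rows | Pooled guided-vs-control rows | Overall rows |
|---|---|---|---|
| Guided, genotype reported | yes | yes | yes |
| Guided, no genotype result | no | no | yes |
| Control | yes | yes | yes |

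This does not depend on which time origin applies.

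**Expected guided events in the gap.** Inputs:
- 160 guided participants (110 + 50, section 2.4.2).
- MACCE probability r = 1–10% (section 3.2.1). No period is stated there; 12 months is assumed.
- Gap g = 3 to 21 days (assumption).
- Constant hazard (assumption).

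Expected events ≈ 160 × r × g/365.
- Lowest: 1.6 × 3/365 = 0.01.
- Highest: 16 × 21/365 = 0.92. The exponential form gives 160 × [1 − 0.9^(21/365)] = 0.97.

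**Relative risk when treatment has no effect**, if controls start at randomisation and guided participants g days later. Let λ = −ln(1 − r).
- Full 12 months from each group's own start, constant hazard: equal observed time, so RR = 1.00.
- Common end date, constant hazard: RR = [1 − exp(−λ(365 − g)/365)] / r.
- Front-loaded hazard: suppose the first 30 days carry k = 3 to 10 times the later hazard and r = 5–10% (assumptions). Let h = λ/(30k + 335) and H(t) = h[k·min(t,30) + max(t − 30, 0)]. With own start, RR = {1 − exp[−(H(365+g) − H(g))]}/r. With a common end, replace H(365+g) by H(365).

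| Setting | g = 7 days | g = 14 days |
|---|---|---|
| Constant hazard, own 12 months | 1.00 | 1.00 |
| Constant hazard, common end | 0.98 | 0.96 |
| Front-loaded, own 12 months | 0.90–0.97 | 0.81–0.94 |
| Front-loaded, common end | 0.89–0.95 | 0.78–0.91 |

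For constant hazard with a common end, 3 days gives 0.99 and 21 days about 0.94.

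**Direction of the missing-arm problem.** Take 8 events in 160 (5.0%) as an illustration. Dropping one participant with an event gives 7/159 = 4.4%, which favours guidance. Dropping 8 event-free participants (5% without a result, an assumption) gives 8/152 = 5.3%, which goes the other way.

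**The case against.** The strongest reply is that the asymmetry in the follow-up window is not written anywhere. The start of the study intervention is undefined in both groups. Section 1.1 describes the investigational product as a selection assay, so the guided intervention could be taken to begin at the genotyping step. Appendix 2 ticks genotyping in the Randomization column. Section 2.5.4 discloses results only after randomisation and genotyping, which leaves room for a similar delay in controls. Sections 1.4.3 and 2.4.2 would place events in the gap inside the window. All of this stands. A reader might infer an established immortal-time bias, with early events counted in controls and excluded in the guided group. The documents support that only as one possible reading, because the control start date is not given.

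Three further inferences go too far.
- That guided participants without a report leave the analysis altogether: Appendix 3 has overall rows whose denominator is all study participants, and section 3.3 keeps data collected before withdrawal.
- That every endpoint is tilted towards guidance: losing event-free participants raises the guided rate, and under constant hazard with equal follow-up the window causes no bias.
- That a lost event is likely: even at 10% risk and 21 days, fewer than one is expected. Section 3.2.1's 1–10% covers a broad list of events and is not a death rate. Entry up to 12 weeks after PCI also means that a front-loaded hazard from randomisation cannot be taken for granted.

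Finally, a sample already drawn might be tested late and used to classify the participant. The plan neither requires nor excludes this, and it would not help after a failed assay.

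None of these replies supplies an arm-level or pooled row for a guided participant who never gets a result.

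**Conclusion.** The concern holds in two parts of different strength. The firm part is that the anchors conflict, none is stated to be randomisation, and the Appendix 3 guided group excludes randomised participants without a genotype result, while the control group has no matching exclusion. The conditional part is that, if controls start at randomisation, guided events before the report also fall outside the Synopsis window.

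The likely size is small but cannot be fixed from the documents. It depends on the assumed turnaround, on reading the 1–10% as a 12-month risk, and on the shape of the hazard. The relative-risk results also assume that controls start at randomisation. In the scenarios examined, bias from the window is either nil or in favour of guidance; bias from missing participants can go either way. The point deserves correction because few events are expected and the repair is cheap, but it does not by itself invalidate the trial. Confidence is moderate.

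**What to change.** - Synopsis, Follow-up: make the date of randomisation time zero for all participants, and reconcile sections 1.4.3 and 2.4.2 with it.
- Count every endpoint event from randomisation to 12 months in both groups.
- Appendix 3, aggregated rows: define the guided group as all participants randomised to genotype guidance, including those with no genotype result. The genotype-specific rows can stay, with the number without a result reported beside them.
- Record the date of the genotype report and the date of treatment selection as descriptive variables, so that the length of the gap is known.

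The cost is wording and two date fields. No patients, visits or tests are added, and the planned 240 is unaffected. Guided-group rates may look slightly less favourable than under the current definitions.
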